7.10. Safety Evaluation

All adverse events (AE) will be coded using the Medical Dictionary for Regulatory Activities (MedDRA) and categorized by System Organ Class (SOC) and Preferred Term (PT) for summary. Device-related AEs, procedure-related AEs, and serious AEs will be tabulated separately and by time period. The denominator in event rate calculation will be based on the number subjects available at the beginning of each time period. The relationship to device and procedure as well as seriousness will be based on site-reported data from the AE case report form (CRF).

The survival from all-cause mortality and aneurysm-related mortality over one year time or longer will be described by the Kaplan-Meier survival curve and the associated Kaplan-Meier estimate will be calculated along with its standard error using the Greenwood method.

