#### L.3.3.2 Subject accountability

Subjects already enrolled and willing to extend their follow-up from 12 to 60 months are to be re-consented. Re-consenting is to occur at or prior to the 12-month follow-up visit. Enrolled subjects who decline to continue to participate in follow-up beyond 12-months shall exit the study upon the completion of their 12-month visit.

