Subjects will be followed until the last subject enrolled has completed the 1 year follow-up visit or until PMA approval is obtained in the US (whatever is later), however, Medtronic will work with FDA to determine if longer term follow after PMA approval is required. A post-approval analysis of 1-year Major Device Event (MDE) rate is planned.

6. Determination of Sample Size

One hundred (100) enrolled subjects will ensure 87 evaluable subjects at 30 days. The primary endpoint analysis will be completed upon 87 evaluable subjects reaching the 30 day endpoint. Based on Valor II study results, Valiant Evo is expected to perform similarly and have 6% of MDE combined with access and/or deployment failures at 30 days. The sample size of 87 evaluable subjects will provide 85% statistical power for the study hypothesis. The type I error is controlled at the one-sided 0.025 level.

Table 1: Power Analysis

True rate of MDEs combined with access and/or deployment failures at 30 day with Valiant Evo	6%
Performance Goal	16%
Significance level	0.025
Statistical test	One-sided binomial test
Evaluable sample size	n=87
Enrollment	Minimum of 100 subjects enrolled to ensure 87 evaluable subjects
Statistical power from the 87 evaluable subjects	85%

One hundred (100) enrolled subjects will also ensure 63 evaluable subjects at 1-year on MDE rate for the post-approval analysis. The VALOR II study with the Valiant stent graft system enrolled 160 patients with DTAA and was assessed through 12 months for purposes of PMA (P100040) approval. Through 1-year post-

treatment, the rate of MDEs combined with access and/or deployment failures was 7.1% (11/153) (Medtronic internal data using the Valiant Evo proposed definition). Therefore, for the purpose of post approval analysis, the rate of MDEs combined with access and deployment failures at 1-year with Valiant Evo is estimated to be 7.1% (refer to Table 22 below for power analysis assumptions).

Table 2: Power Analysis for Post-approval Analysis of 1-year Endpoint

Estimated rate of MDEs combined with access and/or deployment failures at 1 year with Valiant Evo	7.1%
Performance Goal (PG) at 1-year	20%
Significance level	0.05
Statistical test	One-sided binomial test
Evaluable sample size	N = 63 at 1 year
Enrollment	IDE cohort will enroll a minimum of 100 subjects and is expected to have a minimum of 63 evaluable subjects at 1-year follow up.

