- Aneurysm-Related Mortality within 365 days
- MDEs within 365 days
- All AEs within 365 days including:
 - MAEs
 - SAEs
- Secondary procedures within 365 days
- Loss of stent graft patency within 12 months based on imaging findings
- Endoleaks at 12 months based on imaging findings
- Stent graft migration at 12 months as compared to 1-month imaging
- Aneurysm expansion > 5mm at 12 months based on imaging findings relative to the 1-month visit

Secondary endpoints are to be assessed beyond 12 months. The following secondary endpoints are to be evaluated at 24, 36, 48, and 60 months:

- All-cause mortality
- Aneurysm-Related Mortality
- MDEs
- All AEs and SAEs
- Secondary procedures
- Loss of stent graft patency based on site reported imaging findings
- Endoleaks based on site reported imaging findings

- Stent graft migration as compared to 1-month imaging
- Aneurysm expansion > 5mm based on site reported imaging findings relative to the 1-month visit

Health-related quality of life outcomes are to be assessed at all scheduled follow-up visits using the EQ-5D questionnaire.

Stent graft migration will be determined by the core lab or site imaging case report from (CRF). Core lab assessment and site reported result will be analyzed separately. Aneurysm expansion will be calculated. When 1-month image is not available, the latest image taken prior to 1-month will be used for calculation.

Descriptive statistical analyses will be performed on secondary endpoints. No inferential statistical analysis is planned for secondary endpoints.

Non-image endpoints event rates such as mortality, secondary procedures, MAEs, SAEs, conversion to open surgery, and thoracic aortic aneurysm ruptures through 1 year will be calculated in the same way as the MDE rate, specified in Table 5. The event rates beyond 1 year through 5 years will be analyzed using Kaplan Meier method.

Imaging based Event Rate Calculation:

Unless otherwise specified, imaging assessment will be performed by site as well as the core lab. Assessments from the core lab will be the primary result for the PMA and PMA-s submissions and analyzed separately from those by site. Imaging based event rate will be calculated using statistical analysis windows as follows (Table 6):

Table 6: Imaging based Event Rate Calculation:

Event rate = m/n	At 1 Month	At 6 Months	At 12 Months

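### SAP 7.10 divides by-period AE counts by the number at the start of each period, which biases the rates low when subjects are lost, and SAP 7.9 uses a different rule for SAEs that is biased high

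*SAP*

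**What the plan says.** SAP 7.10 (Safety Evaluation) sets up the tables: "Device-related AEs, procedure-related AEs, and serious AEs will be tabulated separately and by time period". It then fixes the divisor: "The denominator in event rate calculation will be based on the number subjects available at the beginning of each time period". It gives no period cut-points and no censoring, exposure or life-table adjustment.

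SAP 7.9 (Evaluation of Objectives) has a different rule for endpoint rates. Rates for mortality and for "secondary procedures, MAEs, SAEs, conversion to open surgery, and thoracic aortic aneurysm ruptures through 1 year will be calculated in the same way"; the formula it points to is the one Table 5 gives for MDEs, m/(m + k). At 365 days, m is the number of subjects with an event on Day 0-365, and k is the number without an event who have been in study at least 305 days. Beyond 1 year, SAP 7.9 uses Kaplan-Meier for non-image events.

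The only figures in the SAP that bear on loss are in Section 6 (Determination of Sample Size): "One hundred (100) enrolled subjects will ensure 87 evaluable subjects at 30 days" and "One hundred (100) enrolled subjects will also ensure 63 evaluable subjects at 1-year on MDE rate for the post-approval analysis". Table 2 says the cohort "is expected to have a minimum of 63 evaluable subjects at 1-year follow up".

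Protocol L.3.3.2 adds an exit point for the International cohort: subjects who decline the extension "shall exit the study upon the completion of their 12-month visit". Protocol Table L-1 puts that visit at Day 305-425.

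**The concern.** Most adverse events can be recorded only while a subject is in the study. A denominator fixed on the first day of a period gives full weight to someone who leaves on its tenth day, although later events in that person cannot enter the numerator. The ratio is then lower than the risk over the period, and the gap grows with the length of the period and the amount of loss.

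Serious AEs are caught by two rules. SAP 7.10 keeps early leavers in the denominator as if fully observed. Table 5 removes early leavers who had no event but keeps those who had one. The first rule errs low and the second errs high. A reader of the clinical study report could meet two SAE percentages for the same subjects and the same year, with no statement of which one to rely on.

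**Working it through.** **Plan's own figures.** The SAP states no bias, so its planning numbers come first. An exact one-sided binomial test with n = 87 (6% against 16%, alpha 0.025) rejects at 7 or fewer events and has power 84.9%; the SAP says 85%. With n = 63 (7.1% against 20%, alpha 0.05) power is 92.3%; the SAP says 92%. The allowances are 1 - 87/100 = 13% at 30 days and 1 - 63/100 = 37% at 1 year.

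**Worst case for 7.10: every non-evaluable subject is a loss.** With n at the start, w leaving evenly over the period and events spread evenly, observed time is about n - w/2. The understatement is therefore w/(2n).

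| Period (assumed) | n to end | w/(2n) |
|---|---|---|
| Day 0-30 | 100 to 87 | 13/200 = 6.5% |
| Day 31-365 | 87 to 63 | 24/174 = 13.8% |
| Day 0-365, one-stage loss | 100 to 63 | 37/200 = 18.5% |

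A constant-hazard model of first event and dropout gives 13.0% to 14.4% for Day 31-365, for true risks of 50% down to 7.1%.

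If the single Day 0-365 period follows both planning points (13 lost by Day 30, then 24), the mean number at risk is (93.5 x 30 + 75 x 335)/365 = 27,930/365 = 76.5 of 100. With a constant hazard and a true 1-year risk of 20%, about 15.4 first events are observed per 100 enrolled. SAP 7.10 would then show 15.4%, which is 1 - 15.4/20 = 23% low.

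**How the size moves (all assumed).**
- Splitting Day 31-365 at Day 183 with linear loss gives 87 to 76.0 to 63, and understatements of 6.3% and 8.6%.
- If half of the events fall at the start of the period, the three table figures halve, to 3.3%, 6.9% and 9.3%.
- With milder loss, 100 to 95 to 85, the mean at risk over Day 0-365 is (97.5 x 30 + 90 x 335)/365 = 90.6, or about 9% low.

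**Table 5 on the same subjects.** Keep the two-stage loss and the true 20% risk. Then m = 15.4. For k, the 63 who stay contribute 63 x 0.80 = 50.4 event-free. About 4.3 leave between Day 305 and Day 365 (24 x 60/335), of whom about 3.5 are event-free. So k is about 53.9, and m/(m + k) = 15.4/69.3 = 22.2%, about 11% too high. The same data give 15.4% under 7.10 and 22.2% under 7.9.

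**Year 2, International cohort only.** Assume that a period starts at Day 366, that a share d declines the extension, and that 12-month visits are uniform over Day 305-425. Half of the decliners are then seen after Day 365 and contribute 30 days on average. The observed fraction is [(1 - d) + (d/2)(30/365)]/(1 - d/2), which is 0.95, 0.90, 0.84 and 0.77 for d = 10%, 20%, 30% and 40%. Pooled with an equal number of fully observed US subjects, the understatement at 20%, 30% and 40% falls from 10%, 16% and 23% to about 5%, 7% and 10%. The documents give no value for d.

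**The case against.** The strongest reply is that the size cannot be read from the SAP. A reader might infer that the SAP expects 37% attrition and that its AE rates will therefore be 13-23% low. The documents do not support this. The 87 and 63 are minimum evaluable numbers for sample-size purposes, not forecasts of loss, and evaluable does not mean still in study. Under Table 5 an event-free subject counts at 30 days after one day in study, and at 365 days after 305. A gap of 13 at Day 30 therefore cannot be taken as 13 withdrawals spread over the month. The 23% also needs a single Day 0-365 period, although 7.10 tabulates by period. Procedure-related events are likely to cluster near Day 0, where little is lost. This objection stands against the size, not against the direction.

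A reader might also infer that all AE and SAE rates are too low, or that risk will falsely appear to fall over time. Neither is established. Endpoint rates through 1 year follow Table 5, and later non-image rates follow Kaplan-Meier. Resetting the denominator at each period already removes earlier leavers. The year-2 effect disappears if the period starts later: with the Day 549 start of the 24-month window in SAP Table 3, which is written for imaging, the decliners would no longer be in the denominator.

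Two narrower points stand. Protocol F.1, F.2.2 and F.2.4 keep recording SAEs for treatment failures and conversions for the whole trial, so those subjects are not lost for SAEs. A subject who dies is not unobserved in the way a withdrawn subject is, so deaths should stay in the denominator.

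**Conclusion.** The point holds on direction and on the inconsistency; its size is conditional. SAP 7.10 biases by-period rates of device-related, procedure-related and serious AEs low whenever subjects withdraw or are lost within a period. With short periods, mild loss or early events the effect is a few percent. About 13-14% for Day 31-365 and about 18-23% for one Day 0-365 period are upper values. They require the whole 100/87/63 allowance to be true loss, leavers spread evenly within each stage, and a roughly constant hazard. Year-2 decliners would add to the bias only if a period starts at Day 366, in one cohort, by an amount that depends on the unknown decline rate.

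The conflict between 7.9 and 7.10 on SAEs through 1 year follows from the text and needs no assumption about size. The tables are descriptive, so no test, power figure or performance goal is affected. It should still be corrected, because these tables inform the safety reading of the submission and the SAP already handles censoring elsewhere.

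**What to change.** In SAP 7.10:

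1. Define the periods by day, including where year 2 starts.
2. Use a denominator that allows for withdrawal and loss. One option is the start number minus half of those withdrawn or lost in the period, with deaths kept in the denominator. The other is cumulative incidence with censoring at last contact and death as a competing event.
3. Show subject-years for each period beside the counts.
4. Use one estimator for SAE rates in 7.9 and 7.10.

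The cost is SAP wording and modest programming on data already collected. The displayed rates will be slightly higher than under 7.10 as written, and the tables will compare less directly with simple n/N tables in earlier submissions. Showing subject-years and the raw counts eases that comparison.

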## F.6 Adverse events

### F.6.1 Definition/classification

For the purposes of the clinical report, Medtronic will classify each Adverse Event according to ISO 14155:2011.\* In case country specific definitions and safety reporting regulations are stricter than mandated per ISO 14155:2011, reporting will be done in compliance with the country specific safety regulations.

All adverse events that meet the study definitions will be reported to the sponsor and documented on the Adverse Event eCRF and in the subject’s medical records.

Clinical events that are inherent to a surgical procedure and expected to occur in the majority of subjects for a projected duration may be considered unavoidable. Such events are listed in Table F-3. These events should not be to be reported as adverse events during this study.

\*: For example, the definition of Serious Adverse Event (SAE) in Germany per the MPSV, § 2 nr 5 is the following:

Serious adverse event is any adverse event, which occurs in an approved clinical investigation or performance evaluation and which has led, might have led or could lead directly or indirectly to the death or any serious deterioration in the state of health condition of a subject, a user or any other person without considering if the event has been caused by the medical device.

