*NOTE 1:* Planned hospitalization for a pre-existing condition, or a procedure required by the CIP, without serious deterioration in health, is not considered a serious adverse event.

**Serious Adverse Device Effect (SADE):** (ISO 14155:2011 3.36)

Adverse device effect that has resulted in any of the consequences characteristic of a Serious Adverse Event

**Unanticipated Serious Adverse Device Effect (USADE):** (ISO 14155:2011 3.42)

Serious adverse device effect which by its nature, incidence, severity or outcome has not been identified in the current version of the risk analysis report

*NOTE:* Anticipated serious adverse device effect (ASADE) is an effect which by its nature, incidence, severity or outcome has been identified in the risk analysis report.

**Unanticipated Adverse Device Effect (UADE):** (21CFR812.3)

Any serious adverse effect on health or safety or any life-threatening problem or death caused by, or associated with, a device, if that effect, problem, or death was not previously identified in nature, severity, or degree of incidence in the investigational plan or application, or any other unanticipated serious problem associated with a device that relates to the rights, safety, or welfare of subjects.

*NOTE:* Although the collection of UADEs is a US 21CFR812.3 requirement, any event from the Valiant Evo International Clinical Trial that meets the UADE criteria will be reported as such and will be adjudicated by the Clinical Event Committee (CEC) in order to be pooled with data collected during the concurrently enrolling IDE trial.

**Device deficiency:** (ISO 14155:2011 3.15)

Inadequacy of a medical device with respect to its identity, quality, durability, reliability, safety or performance

*NOTE:* Device deficiencies include malfunctions, use errors, and inadequate labelling.

**For the Valiant Evo International Clinical trial Medtronic has defined Major Device Effects (MDEs) which will be used to assess the primary endpoint.**

MDEs include the occurrence of any of the following and are defined in Appendix L.2.1:

- Device-related secondary procedures
- Device-related mortality
- Conversion to open surgery
- Thoracic aortic aneurysm rupture

**For the Valiant Evo International Clinical trial Medtronic has defined Major Adverse Events which will be used to assess the secondary endpoints.**

MAEs include the occurrence of any of the following and are defined in Appendix L.2.2:

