### *F.6.5 Potential Complaint Reporting*

Potential complaints sourced from the study are reported to the Global Complaint Handling Unit (GCH)

Potential complaints may be found throughout clinical study data as reported on CRFs and reviewed, or potential complaints may be learned about in alternative fashions within source documents or in discussions with investigational site staff. Potential complaints are considered for the following:

- All adverse events collected deemed related to the procedure/product/therapy
- All product deficiencies or technical observations, if applicable
- All deaths deemed related to the procedure/product/therapy

Relationship is to be determined by the investigator and the sponsor. The CEC will assess relationship for adjudicable events only.

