#### *F.6.6 Clinical Event Committee*

A clinical event committee (CEC) will be established. The CEC is an independent committee made up of clinicians (interventional) with pertinent expertise who are not participants in the study and who do not have any other real or potential conflicts of interest. The CEC will meet periodically to review and adjudicate all MDEs, deaths and all DTAA ruptures that occur throughout the conduct of the clinical trial. A charter will be developed that will detail the criteria for selected complications and clinical events that need to be adjudicated as well as the CEC composition, duties, procedures and adjudication rules and meeting frequency.

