## L.2 Definitions

### L.2.1 Primary and Secondary Endpoints

Term	Definition
Access failure	Inability to insert device due to mechanical failure or anatomic exclusions of the femoral or iliac arteries
Deployment Failure	Deployment failure due to subject anatomy or mechanical failure. This specifically refers to deployment of the stent graft from the delivery system.
Adverse Event (AE)	See section F.6.1
Serious Adverse Event (SAE)	See section F.6.1
Major Adverse Events (MAEs)	
Major Adverse events include the occurrence of any of the following :
 
 
• Respiratory complications: atelectasis/pneumonia, pulmonary embolism, pulmonary edema, respiratory failure.
 
• Renal complications: renal failure, renal insufficiency.
 
• Cardiac complications: myocardial infarction (MI), unstable angina, new arrhythmia, exacerbation of congestive heart failure (CHF).
 
• Neurological complications: new cerebrovascular accident (CVA), cerebrovascular embolic events, paraplegia, paraparesis.
 
• Gastrointestinal complications: bowel ischemia.
 
• Major bleeding complication (procedural or post-procedural), coagulopathy.
 
• Vascular Complications: aortic rupture, aneurysm rupture, hematoma at access site, pseudo or false aneurysm, arteriovenous (AV) fistula, retroperitoneal bleed, limb ischemia, thrombosis.
 
 
See definition of terms in section L.2.2

Major Device Effects (MDEs)	
Major Device Effects include the occurrence of any of the following:
 
 
• Device-related secondary procedures
 
• Device-related mortality
 
• Conversion to open surgery
 
• Thoracic Aortic Aneurysm rupture
 

Device-related mortality	
Any death related directly to the implantation, the presence, or operation of the investigational device in the medical opinion of the Clinical Events Committee (CEC).
 
Deaths following complications that are associated with the

Term	Definition
	device design as it relates to placement, efficacy or durability (these may involve the implanted device or the delivery system), with endoleak, device migration, and failure to cover the aortic injury are included in this definition.
Peri-operative mortality	All deaths occurring intra-operatively and within 30 days from the primary procedure
All-cause mortality	Death from any cause

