Aneurysm-related mortality (ARM)	
Any death occurring within 30 days from either the initial procedure or any secondary procedure intended to treat the aneurysm will be considered ARM unless there is evidence to the contrary. Additionally, deaths occurring as a consequence of any procedure intended to treat the targeted aneurysm, aneurysm rupture, or a conversion to open repair will also be considered as ARM.
 
Ultimate adjudication of relatedness of death will be made by the Clinical Events Committee (CEC). Excluded are aneurysms in anatomic areas other than the targeted segment treated by the Valiant Evo Thoracic Stent Graft System.

Device-related secondary procedure	
Any secondary procedure that is determined by the investigator to be clearly related to any of the implanted stent graft components.
 
Ultimate adjudication of relatedness of secondary procedure will be made by the Clinical Events Committee (CEC).

Secondary procedure	Any endovascular or surgical procedure performed following the completion of the operative initial implantation procedure (thus on subsequent occasion after final closure of the last artery access site) which involves the targeted vascular segment treated by the Valiant Evo Thoracic Stent Graft System in which there is either manipulation of the existing Valiant Evo Thoracic Stent Graft, implantation of any additional stent graft devices or manipulation of covered branch(es) by implanted stent grafts.
Conversion to open surgery	
Primary Conversion: Conversion from endovascular to open repair required at the time of the original procedure, to treat the lesion intended to be treated with the Valiant Evo Thoracic Stent Graft System.
 
Secondary Conversion: Conversion from endovascular to open repair required at a time beyond the initial endovascular procedure, to treat the lesion originally treated with the Valiant Evo Thoracic Stent Graft System.

Thoracic Aortic Aneurysm rupture	
Rupture or perforation of the targeted thoracic aneurysmal sac as detected by angiography, CT scan, or direct observation at surgery or autopsy.
 
Aneurysm rupture should be reported as either procedure-

Term	Definition

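### SAP 7.10 takes the relatedness and seriousness of AEs from the site CRF alone, with no rule for events on which the CEC or the sponsor decides differently

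*SAP*

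**What the plan says.** SAP 7.10 plans three sets of tables: "Device-related AEs, procedure-related AEs, and serious AEs will be tabulated separately and by time period". It then names one source for the attributes that define them: "The relationship to device and procedure as well as seriousness will be based on site-reported data from the AE case report form (CRF". Neither the sponsor nor the CEC is mentioned there.

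The International protocol spreads these judgements more widely:

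- **Sponsor (F.6.1):** "For the purposes of the clinical report, Medtronic will classify each Adverse Event according to ISO 14155:2011".
- **Relationship (F.6.5, on complaint reporting):** "Relationship is to be determined by the investigator and the sponsor. The CEC will assess relationship for adjudicable events only".
- **CEC scope (F.6.6):** the committee is to "review and adjudicate all MDEs, deaths and all DTAA ruptures that occur throughout the conduct of the clinical trial", with further criteria left to a charter. Under the UADE definition in F.6.1, events meeting those criteria "will be adjudicated by the Clinical Event Committee (CEC) in order to be pooled with data collected during the concurrently enrolling IDE trial".
- **CEC as final judge (L.2.1):** a death is device-related if it is so "in the medical opinion of the Clinical Events Committee (CEC". For secondary procedures the investigator judges first, but "Ultimate adjudication of relatedness of secondary procedure will be made by the Clinical Events Committee (CEC".

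SAP 7.9 has all MDEs adjudicated by the CEC and builds the MDE rate on that.

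**The concern.** The report will contain two statements about device-related harm that rest on different judges. The MDE rate rests on the CEC; the device-related AE table rests on the site. The SAP has no rule of precedence and no listing that would show where the two disagree.

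The trial is open-label and single-arm, so the site that implanted the device also attributes the event. In a first-in-human study, the device-related AE table is one of the first things a regulator or clinician reads. If it disagrees with the adjudicated MDEs and nothing explains why, both lose credibility.

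Seriousness is involved too. SAEs are a listed secondary endpoint at 30 days and 12 months, and the 7.10 sentence is the SAP's only statement of where seriousness comes from.

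For imaging the SAP does the opposite: SAP 7.9 makes core lab readings the primary result for the submissions and analyses site readings separately. No reason is given for treating AE attribution differently.

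**Working it through.** The plan gives no figure to reproduce, so the check is a comparison of provisions followed by simple arithmetic on the weight of one subject.

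**Step 1. Who decides what**

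| Judgement | International protocol | SAP |
|---|---|---|
| Device-relatedness of a death | CEC opinion (L.2.1) | CEC for the MDE rate (7.9); site for the AE table (7.10) |
| Device-relatedness of a secondary procedure | Investigator first, CEC final (L.2.1) | CEC for the MDE rate (7.9); site for the AE table (7.10) |
| Relatedness of other AEs | Investigator and sponsor; CEC only if adjudicable (F.6.5) | Site (7.10) |
| Seriousness | Sponsor classification under ISO 14155 for the clinical report (F.6.1); no CEC role stated | Site (7.10) |

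The ISO categories defined in F.6.1 (ADE, SAE, SADE, USADE) turn on device relation, seriousness or both. The sponsor's classification therefore covers the same attributes that 7.10 takes from the site.

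**Step 2. Where the two SAP sections can contradict each other**

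An MDE has four components. Two depend on relatedness: device-related secondary procedure and device-related mortality. The other two, conversion to open surgery and thoracic aortic aneurysm rupture, count whatever their cause. A direct contradiction over device-relatedness is therefore possible for two of the four.

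**Step 3. Following the plan exactly**

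- The site marks the AE behind a death as not device-related and the CEC judges the death device-related. Under SAP 7.9 the subject counts as having an MDE. Under SAP 7.10 the event is absent from the device-related table.
- The site marks the AE behind a secondary procedure as device-related and the CEC decides otherwise. The procedure is not a device-related MDE, but the event stays in the device-related table.

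Both outcomes comply with the SAP as written.

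**Step 4. Weight of one discordant subject**

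With a full-cohort denominator, and if the subject has no other event counted in that row:

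- International cohort: 1/47 = 0.021, or 2.1 percentage points.
- Combined cohort planned in SAP section 6: 1/100 = 0.010, or 1.0 percentage point.

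SAP 7.10 uses as denominator those still available when each period starts, so the weight is somewhat larger in later periods. These figures show the weight of any single subject. They do not estimate how many events will be discordant.

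**The case against.** The strongest reply is that site attribution is a source the protocol itself recognises. F.6.5 names the investigator, and F.5 requires sites to document seriousness and relation to the device. F.6.1 says that the sponsor classifies, not that it overrides the site, so the ISO categories might simply be derived from the site's entries. The sentence giving the sponsor a role in relationship sits under complaint reporting, not analysis. There are also checks on the data: queries go back to the investigator (G.1.4), and an Independent Medical Monitor reviews events case by case (F.6.7). Finally, the SAP names the US protocol as its primary resource. That protocol and the CEC charter are not among the documents.

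Much of this stands. It is why site attribution should remain the basis for AEs that the CEC does not adjudicate, and why an independent sponsor override is an inference. The data checks make discordance less likely but do not resolve it when it occurs. The unseen US protocol limits the comparison, but does not remove it. International subjects may supply up to half of the PMA data (SAP section 5), and SAP 7.3 assumes a single CEC for both trials.

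The reply does not answer the conflict over deaths and secondary procedures. There the protocol names a final judge, and 7.10 states a rule that uses a different one.

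A reader might also infer more than the documents support:

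- *That the CEC decides relatedness for AEs in general.* F.6.5 limits it to adjudicable events, so most rows of the 7.10 tables will have no CEC decision.
- *That the tables will mainly understate device-related harm.* The CEC can overrule the investigator in either direction, and the documents give no data on which is commoner.
- *That a SADE count will be too low.* SAP 7.10 plans no separate SADE table.

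**Conclusion.** The point holds as an inconsistency in the descriptive safety tables. For device-related deaths and secondary procedures, SAP 7.10 uses a different judge from the one the protocol makes final and SAP 7.9 uses, so one report can contradict itself. For other AEs, the SAP leaves out the sponsor classification that the protocol says is made for the clinical report.

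It would be wrong to conclude that the MDE rate, the 30-day primary endpoint or its power is at risk. SAP 7.9 takes MDEs from CEC adjudication, and none of these uses the 7.10 attribution.

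The size is 2.1 points (1/47) or 1.0 point (1/100) per discordant subject, on the conditions given with the arithmetic. The number and direction of discordant events are unknown.

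The conclusion rests on two assumptions: that the US protocol and the CEC charter contain no reconciling rule, and that a death or secondary procedure can be traced to an AE record in the 7.10 tables. The change is worth making before the tables are produced because it is cheap and reduces reliance on the implanting site's attribution.

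**What to change.** Replace the attribution sentence in SAP 7.10 with wording such as:

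> Where the CEC has adjudicated the device-relatedness of an event (deaths, secondary procedures and other adjudicable events), the CEC decision is used in the device-related AE table. For all other AEs, site-reported attribution is used, and the sponsor's ISO 14155 classification of relatedness and seriousness is shown beside it. Events on which site, sponsor and CEC differ are listed.

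Three details to settle at the same time:

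- Confine the CEC rule to device-relatedness. The documents state no CEC role in seriousness, and its stated role does not extend to procedure-relatedness of AEs in general.
- Say how a CEC decision on a death or secondary procedure is linked to the AE record that led to it.
- Confirm against the US protocol and the CEC charter that the rule fits both, and that the CEC decisions and sponsor classifications are held as analysable data. The protocol provides for them but does not show how they are stored.

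The cost is SAP wording, an added display of the sponsor's classification and one extra listing. The device-related or serious rates shown may be slightly less favourable than the site-only figures.
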